The primary official permission will be obtained from the research ethics committee of faculty of nursing, Cairo University to approve the tools and the study. Also, the investigator will explain to the women the purpose and nature of the study and its importance. In addition, informed written consents will be obtained from women who were willing to participate in the study after ensuring that their participation is voluntary and the trial posed no risk or hazards on them. As well, each woman will be assured that she has the right to withdraw of the trial at any time without any effect on her care. Then, confidentiality will be assured through coding of data by the investigator and keeping the data in a secret place.

Validity and reliability

Un standardized tools were submitted to 3 experts in the field of maternity nursing to test content validity, clarity of sentences and an appropriateness of content. Modifications were carried out according to the expert judgment.

Procedure

First, the primary official permission will be obtained from the research ethics committee of faculty of nursing, Cairo University to approve the tools and the study. An official permission will be granted from the hospital administrative personnel in the recommended setting to collect the data. Then, data collection will be carried out through five steps in each group: Recruitment & randomization; interviewing; initial assessment; intervention; follow up and monitoring.

Recruitment and Randomization of sample: Women who will meet the eligibility criteria will be recruited from a written list done by the investigator every day. Those plotted in the odd number will be selected until completion of the sample. Random assignment of the subjects into two groups will be done through an opaque sealed envelope reflecting the type of each group, and then the eligible women will be asked to choose an envelope to

determine their groups.

Interviewing: During interview the aim of study will be explained to the women in both groups (study & control group) to gain their acceptance to participate in the study then data related to socio-demographic status and obstetric history will be collected from both groups

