Initial Assessment: Initial assessment for women in both groups (study & control group) will be carried out in relation to body mass index (BMI), type of perineal trauma after delivery (episiotomy, or tears), degree of perineal tear (1st or 2nd degree tear), and assessment of perineal trauma condition will be done using standardized REEDA scale . Also, women will be asked to indicate the degree of perineal pain using Visual Analogue Scale for pain intensity (VAS).This assessment will take 15 minutes for each woman.

Intervention:

Intervention for the study group: For the study group the intervention will be according to a designed protocol of care that entails; 1) Application of ice gel pad on perineal trauma for the first 24 hours post partum; 2) Performance of pelvic floor exercises (Kegel exercises) from six hours till one week postpartum; 3) Application of warm compresses after 48 hours and through the first week postpartum. The investigator will perform demonstration and then redemonstration by the women on each intervention will be done. A designed booklet (developed previously) that explains each intervention will be given to each woman.

Immediately after delivery (within 30 minutes to one hour after delivery), an ice gel pad will be applied to perineal trauma. It will be available in an individual package(every woman will alternate between two ice gel pads); each gel pad will have fixed standardized diameter (an approximately 5 cm width, 23 cm length, and 1.5 cm thickness) and approved by Egyptian ministry of health. It will be kept in the freezer for 45–60 minutes and

will be removed when frozen. Then, it will be wrapped in a sterile pad and applied to cover the perineum and anal region. The pad will be compatible with the anatomical structure of the perineum.

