The investigator will provide a clear and concise information through oral and written instructions about the following; 1) The ice gel pad's purpose, benefits, anticipated effects and how to apply it, 2) Apply the ice gel pad on perineum after birth within 30 minutes to an hour, 3) Instruct the women to apply the ice gel pad for about 20 minutes every two hours during the first 24 hours postpartum only, 4) The perineal pad should be changed regularly every two hours to prevent infection. This session will take 30-40 minutes for each woman. Then, six hours after the ice gel pad application, assessment of experienced perineal pain will be done using Visual Analogue Scale for pain intensity (VAS) and assessment of perineal trauma condition will be done using standardized REEDA scale.

Also, six hours after birth women will receive instructions to practice pelvic floor exercises (Kegel exercises) and will be asked to perform these exercises from 6 hours postpartum and continue at home till one week. Before applying the technique, the investigator will teach the women how to recognize the accurate muscle, whereby she imagines holding passing gases or trying to stop the flow of urine midstream at the same time. The women will be taught to insert a clean finger into the vagina before practicing the exercises and if the women feeling pressure around her finger, she is on the right track, the mother also will be instructed to place a hand on her belly during the exercises to make sure that it is kept relaxed.

The investigator will perform vaginal examination while the woman is doing the pelvic floor exercises (Kegel exercises) to ensure correct use of muscles. The investigator

will instruct the women to continue contracting the muscles for about 5 seconds and then to loosen them for 5 seconds and repeat it for five times each set, perform at least five sets per day (total 25 contractions each day will be performed). The mother will be instructed to perform these five sets of exercises at the rest period between other intervention (application of cold compresses for the first 24 hours and application of warm compresses after 48 hours) with at least two hours rest between each set.

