In addition, women will be instructed to apply warm compresses on perineal trauma 48 hours postpartum +at home. This will be done by using a clean pad soaked in warm water and squeezed to remove excess water then placed gently on the perineum, the warm compresses will be applied for 15 minutes three times per day (every 8 hours), and water in the bowl will be replaced with every application. Women will be asked to apply warm compresses on perineal trauma from 48 hours postpartum till one week. Also, before discharge each woman will have an explanation of Visual Analogue Scale for pain intensity (VAS) and they will be trained to indicate level of perineal pain using it. This session will take 30-40 minutes for each woman.

Intervention for the control group: The control group will receive the routine hospital care only. Then, six hours after delivery, assessment of experienced perineal pain will be done using Visual Analogue Scale for pain intensity (VAS) and assessment of perineal trauma condition will be done using standardized REEDA scale.

Follow up and monitoring: Follow up will be done by telephone calls and by postpartum visit at the seventh day:

For intervention group follow up by telephone call will be done at 24 hours to assess the following; degree of perineal pain using Visual Analogue Scale for pain intensity (VAS),

the women compliance with ice gel pad application for the first 24 hours, the women's need for additional analgesia and assess women's postpartum difficulty with performing functional activities as turning/ rolling in bed, getting out of bed, sitting, walking, defecation and urination using Visual Analogue Scale(VAS) for rating functional activities.

Also, telephone follow up will done at third and fifth day postpartum to assess degree of perineal pain using Visual Analogue Scale for pain intensity (VAS) and assess women's postpartum difficulty with performing functional activities as turning/ rolling in bed, getting out of bed, sitting, walking, defecation and urination using Visual Analogue Scale(VAS) for rating functional activities. The investigator will also assess mother compliance with the performance of pelvic floor exercises (Kegel exercises) and application of perineal warm compresses using postpartum follow up sheet.

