For control group follow up by telephone call will be done at 24 hours to assess degree of perineal pain using Visual Analogue Scale for pain intensity (VAS), the women's need for additional analgesia and assess women's postpartum difficulty with functional activities as turning/ rolling in bed, getting out of bed, sitting, walking, defecation and urination using Visual Analogue Scale (VAS) for rating functional activities. Also, telephone follow up will be done at third and fifth day postpartum to assess degree of perineal pain using Visual Analogue Scale for pain intensity (VAS) and assess women's postpartum difficulty with performing functional activities as turning/ rolling in bed, getting out of bed, sitting, walking, defecation and urination using Visual Analogue Scale (VAS) for rating functional activities.

Then, a final postpartum follow up visit for both groups at the seventh day will be conducted for assessment of perineal trauma condition and healing process using

standardized REEDA scale and assess the degree of perineal pain using Visual Analogue Scale for pain intensity (VAS).

References

Davidson, N. (1974). REEDA: evaluating postpartum healing. *J Nurse Midwifery*. 1974; 9:6–9.

Derya, K., Ergul, Senol, &Aslan, E. (2017). The Effects of Cold Application to the Perineum on Pain Relief After Vaginal Birth, *Asian Nursing Research*, Volume 11, Issue 4, Pages 276-282, ISSN 1976-1317.

El-Saidy, T. M. K., Abou shady, R. M. N., &Soliman, H. F. A. (2018). Effect of Applying Crushed Ice Gel Pads on Episiotomy Pain and Wound Healing Among Postpartum Primiparous Women. *ijnd* 2018, 8, 19-29.

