Data were statistically described in terms of mean \pm standard deviation (\pm SD), or frequencies (number of cases) and percentages when appropriate. Because the groups are large enough, comparison of numerical variables between the study groups was done using a student t test for independent samples (including statistical analysis of the primary outcomes as perineal pain scores and perineal trauma healing scores among the study and control groups). For comparing categorical data, the chi-square test was performed (including statistical analysis of the difficulties with functional activities; secondary outcome). An exact test was used when the expected frequency was less than 5. Two sided p values less than 0.05 were considered statistically significant. All statistical calculations were done using the computer programme IBM SPSS (Statistical Package for the Social Sciences; IBM Corp., Armonk, NY, USA), release 22 for Microsoft Windows.

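### Pain is scored at an initial assessment and five later contacts, but the only stated analysis takes one value per woman, so earlier scores do not help when a later one is missed

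*Combined protocol and SAP*

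**What the plan says.** Outcome measures lists severity of perineal pain and delayed healing as the primary outcomes. The pain VAS is scheduled as follows:

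- **Initial Assessment:** both arms, together with REEDA.
- **About 6 hours:** both arms, together with REEDA. The clock differs by arm: "six hours after the ice gel pad application, assessment of experienced perineal pain will be done" in the study group, "six hours after delivery, assessment of experienced perineal pain will be done" in the control group.
- **24 hours:** telephone, both arms.
- **Days 3 and 5:** telephone, both arms. For the control group the text is "telephone follow up will be done at third and fifth day postpartum to assess degree of perineal pain", and the study group has the matching calls.
- **Day 7:** "a final postpartum follow up visit for both groups at the seventh day will be conducted", with VAS and REEDA.

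That is six pain scores per woman, five of them after the initial assessment, and three REEDA scores, two of them after it.

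For analysis, the Statistical plan states that "comparison of numerical variables between the study groups was done using a student t test for independent samples". A bracketed remark there makes clear that both primary outcomes, pain and healing, fall under this test. The plan names no time point, summary across times, repeated-measures term, adjustment for the initial score, analysis set or rule for a missed score. Ethical consideration tells each woman that "she has the right to withdraw of the trial at any time". No dropout allowance appears under Sample.

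**The concern.** Four of the five post-baseline pain scores need a woman to answer the telephone or come back to the hospital in the first week after birth, so some will be missed. An independent-samples t test at day 7 uses only the women scored at day 7. Another woman's scores at 6 hours, 24 hours, day 3 and day 5 are in hand and correlated with the missing one, yet they add nothing to that comparison.

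Two things are at stake. One is precision. The other is bias in a primary outcome, if the women who come back differ from those who do not in a way that is not the same in the two arms. A model fitted jointly to all the scores needs a weaker assumption: that absence is explained by what has already been recorded.

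**Working it through.** The plan gives no figure of its own on this point, so there is nothing to reproduce. The size has to be shown over a range of assumptions.

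**Inputs from the documents.** 50 women per arm (Sample); five post-baseline VAS scores (Procedure); two-sided 0.05 (Statistical plan).

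**Assumed inputs.** VAS SD 2 cm; about 20% missing at day 7; correlation between scores first-order autoregressive at 0.5 or 0.7, or exchangeable at 0.6. The sample-size effect of 80% is read as a standardised difference of 0.8, so the true difference, where one is used, is 0.8 × 2 = 1.6 cm.

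**Step 1: precision when absence is purely random.** Let r be the correlation of the day-7 score with the earlier scores, n = 50 randomised and n_obs = 40 seen at day 7. Then

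effective n = 1 / [r²/n + (1 − r²)/n_obs]

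- r = 0.5: 1 / (0.25/50 + 0.75/40) = 1/0.02375 = 42.1
- r = 0.7: 1 / (0.49/50 + 0.51/40) = 1/0.02255 = 44.3
- r = 0.8: 1 / (0.64/50 + 0.36/40) = 1/0.02180 = 45.9

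The t test on attenders has 40. Neither method is biased here, and with no missing scores the two agree.

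**Step 2: bias when absence depends on recorded pain.** In each arm, the mean of the women present differs from the mean of all randomised women by some shift. The bias of the t-test difference is the study-arm shift minus the control-arm shift. Equal shifts cancel and opposite shifts add.

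This was simulated with day-7 absence logistic in day-5 pain, the odds changing by a factor e per SD. The day-7 t test was compared with a likelihood estimate using the four earlier scores. The ranges below cover several runs with slightly different loss rates.

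| Day-7 absence | True difference | t-test bias (size) | t-test error rate or power |
|---|---|---|---|
| Same mechanism in both arms | 0 | about 0 | false-positive rate about 5% |
| Same mechanism in both arms | 1.6 cm | 0.07 to 0.14 cm, towards no effect | power 0.89 to 0.94 |
| Depends on pain in one arm only | 0 | 0.16 to 0.26 cm | false-positive rate 6.5 to 9% |
| Opposite directions in the two arms | 0 | 0.35 to 0.50 cm | false-positive rate 12 to 22% |

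The last two rows fit together: twice the central one-arm range of 0.18 to 0.24 cm is 0.36 to 0.48 cm. The second row is biased although the mechanism is shared, because treatment lowers pain and so changes who is absent. The likelihood estimate was biased by at most about 0.02 cm in all of these settings.

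**Step 3: where the joint model also fails.** If absence depends on the unrecorded day-7 pain itself, in opposite directions in the two arms, the likelihood estimate is biased by 0.36 to 0.53 cm. With one arm only it is 0.17 to 0.26 cm.

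**Scale.** Against 1.6 cm, a bias of 0.1 cm is 0.1/1.6 = 6%, 0.2 cm is 12.5% and 0.5 cm is 31%.

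**The case against.** The strongest reply is that the harm depends wholly on an amount and pattern of absence that the documents do not give. Both arms have the same calls and the same day-7 visit, and nothing documents opposite reasons for staying away. The precision gain is modest: if the effect size is d = 0.8, 40 per arm still gives two-sided power of 0.942. The comparison in Step 2 also suits the joint model, because absence there depends only on a score that is always recorded. All of this stands. It makes the opposite-direction row a worst case, not a forecast. Arm-specific absence nevertheless remains plausible, since only the study group has teaching sessions, home treatment to day 7 and compliance questions in the calls.

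A reader might also infer four stronger things, which the documents or the calculations do not support:

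- **That the plan prescribes a separate test at every contact.** It does not say so. This is an inference from a test that takes one value per woman and from the absence of any summary measure.
- **That the other scores of a woman who misses a contact are discarded.** On the per-contact reading they still enter the tests at the contacts she attended. They are unused only at the contact she missed.
- **That the t test is biased whenever absence depends on pain.** With the same mechanism in both arms and no treatment effect, the bias is about zero and the error rate about 5%.
- **That a mixed model cures the problem outright.** Step 3 shows that it does not if absence follows unrecorded pain.

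Other methods, such as multiple imputation, or a single named time point with adjustment for the initial score, would also be defensible. The plan currently states none of them.

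**Conclusion.** The point holds in a conditional form. A repeated primary outcome is paired with a test that does not use the repetition, and nothing says how a missed score is handled. On the natural per-contact reading, this costs the equivalent of roughly 2 to 6 women per arm at day 7. It can also bias the day-7 difference by about 0.1 cm, about 0.2 cm or, at worst, about 0.5 cm, depending on how absence works in the two arms. These sizes rest on an assumed SD of 2 cm and about 20% loss. With little or no missing data the issue largely disappears. It is a worthwhile, inexpensive improvement to the plan; it does not show that the trial's result will be wrong.

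**What to change.** In the Statistical plan:

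1. Analyse the five post-baseline VAS scores in one mixed model for repeated measures. Include arm, time as a category, arm × time, the initial VAS and its interaction with time. Use unstructured within-woman covariance and every randomised woman with at least one post-baseline score. Read the arm difference at each planned time from this model.
2. Use the same form for the 6-hour and day-7 REEDA scores, with initial REEDA as the covariate.
3. Keep the t tests as a sensitivity analysis, and say that each uses the women scored at that contact.
4. Add a simple sensitivity analysis for absence that depends on unrecorded pain. For example, shift the imputed missing scores by increasing amounts in one arm and report when the conclusion changes.
5. Report the number of women scored at each contact, by arm.

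The cost is wording and slightly more analysis work, with no new data, visits or patients. The model is a little harder to present and still assumes that scores are missing at random, which is why item 4 is needed. It yields five arm differences, so which of them is primary remains a separate decision for the sponsor.

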From clinical experience, it was observed that many postpartum women with perineal trauma experience several short and long-term physical, physiological, social and psychological postpartum complications such as severe pain, delayed healing of the wound, infection and dyspareunia which may affect the women resumption of function at postpartum period and their future choice of the mode of childbirth. At the same time, there is a lack of statistical documentation on the magnitude of this problem. As well as, there are considerable gaps with implementation of evidence to support management of perineal trauma at postpartum period.

In this context, serious actions should be taken to accelerate the perineal trauma healing and relieve the perineal pain as possible. Most important of these actions is immediate postpartum perineal ice gel pad application, later performance of pelvic floor exercises (Kegel exercises) and perineal warm compresses. These interventions have a lot of advantages as they are not costing, appropriate to postpartum women in many situations, and

safe. Moreover, these interventions promote, accelerate the healing, decrease the perineal pain and facilitate restoration of muscle tone (Farrag, Eswi, & Badran, 2016).

In Egypt, there is a scarce of RCT studies that was conducted in this respect and they have contradicting results. Moreover, almost all these studies were conducted to test only one intervention or compare between two interventions for treatment of perineal trauma but no study tested the impact of a designed protocol of care which starts from immediate postpartum and continues throughout the first week where a combination of therapies is implemented. So, the results of this study will add to the quality of evidence on the effectiveness of postpartum interventions for improving the recovery of postpartum perineal trauma. This protocol may be used as guidelines to be implemented for better quality of patient care.

Aim of the study

The aim of the current study is to test the effect of designed protocol of care on the outcomes of postpartum perineal trauma.

Outcome measures

- **Primary outcomes:** Severity of perineal pain, delayed perineal trauma healing.
- **Secondary outcomes:** Occurrence of infection, postpartum difficulty with turning/rolling in bed, getting out of bed, sitting, walking, defecation and urination.

Research Hypotheses

To fulfill the aim of this study the following research hypothesis is formulated:

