A total of (100) postpartum women with normal spontaneous vaginal delivery and having postpartum perineal trauma will be recruited for this study and randomly assigned to either study group (50) women or control group (50) women. Inclusion criteria will be according to the following; primiparous or 2nd. multiparaous women with postpartum perineal trauma either episiotomy or perineal tear (first and second degree only), age not exceeding 40 years, , body mass index (BMI)within normal 18.5-24.9 kg/m² or overweight 25-29.9 kg/m², free from any high risk condition affecting perineal trauma healing (e.g., diabetes mellitus or obesity), over 37 week gestation and not having any complications during labor and delivery(e.g., abnormal presentation, obstructed labor or delivered with instrument), not having any immediate postnatal complications such as postpartum hemorrhage.

The sample size was calculated using a G-power version 3.1.1 for power analysis. A Power of .95 ($\beta = 1 - .95 = .05$) at alpha .05 (one-sided) was used as the significance level, and effect size= (80%).

Setting

The study will be conducted at postpartum ward of emergency department for labor and delivery in Obstetrics and Gynecology Hospital at Kasr El Aini University Hospital affiliated to Cairo University. Postpartum ward provides care for postpartum women with normal vaginal delivery and post abortion women. The capacity of the ward is 20 beds which provide care for approximately (3000) normal deliveries annually according to local statistics for the year 2020 (Kasr El Aini University Hospital Statistics, 2020).

Tools for Data collection

Required data will be collected by using 5 tools: A) Structured interview schedule; B) Visual Analogue Scale for pain intensity(VAS); C) Visual Analogue Scale (VAS) for rating functional activities; D) Standardized REEDA scale; and E) Postpartum follow up sheet.

Tool (A) Structured Interview Schedule: This tool will be designed by the investigator and will include two sections:

- The first section: Will include four items to assess participants' demographic data such as (age, BMI, educational level, occupation, residence).
- The second section: Will include four items to assess the participants current obstetric history (e.g., obstetric code), type of perineal trauma after delivery (episiotomy, or tears) and degree of perineal tear (1st or 2nd degree tear).

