Tool (B) Visual Analogue Scale for Pain Intensity (VAS): It is a standardized linear scale developed by Freyd et al., (1923). It is a self-reported 10 cm horizontal line which represents the subjective estimation of pain intensity. It comprises 0-10-point numerical scale, the two opposite ends representing no pain to severe pain as follows: no pain (0), mild pain (< 4), moderate pain (4 - <8), and sever pain (8-10). This tool is valid and reliable, test-retest reliability coefficient of the VAS has been demonstrated in several studies as $r =0.62$ (Derya, Ergul, Senol, &Aslan, 2017).

Tool (C) Visual Analogue Scale (VAS) for rating functional activities: This tool is adopted from Karakaya et al.,(2012), the difficulty with performing functional activities as (turning/ rolling in bed, getting out of bed, walking, sitting, defecation and urination) will be evaluated by using horizontal 10 cm visual analogue scale for each functional activity, the scale will be applied six times to measure the difficulty with each activity (VAS will be

marked by the women). The scoring for each activity will be as follows: no difficulty (0), mild difficulty (< 4), moderate difficulty (4 - <8), and sever difficulty (8-10). The total score will be recorded (0-60 point), the lowest score (0) indicate no difficulties and the maximum score (60) indicate maximum difficulty. The total score will be interpreted as the following no difficulties (0), Mild difficulties (1 - < 24), Moderate difficulties (24 - < 48), Sever difficulties (48-60). This tool is valid and reliable, test-retest reliability coefficient has been demonstrated as $r = 0.82$ (Karakaya et al., 2012).

Tool (D) Standardized REEDA Scale: This tool is adopted from Davidson (1974), REEDA scale will be used to assess condition of perineal trauma. REEDA scale is a descriptive scale having a four point categorical score (0-3) that measures five components associated with the healing process of perineal trauma. This includes: Redness, Edema, Ecchymosis, Discharge and Approximation of sutures. The total score ranged from 0 to 15 and categorized as the following; 0 to 2 cm good wound healing with no infection, 3 to 5 cm moderate wound healing, 6 to 8 cm mild wound healing, and 9 to 15 cm poor wound healing with infection . This tool is valid and reliable, test-retest reliability coefficient of the REEDA scale has been demonstrated as $r = 0.70$ (Farrag, Eswi, & Badran, 2016).

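### Functional difficulty is assigned to chi-square, probably on severity bands, although a 0-10 score exists; and infection is defined only by bands of the REEDA total that also measures primary healing

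*Combined protocol and SAP*

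**What the plan says.** **Functional activities.** Outcome measures lists the secondary outcomes as "Occurrence of infection, postpartum difficulty with turning/rolling in bed, getting out of bed, sitting, walking, defecation and urination". Tool (C) uses a "horizontal 10 cm visual analogue scale for each functional activity", completed by the woman herself, and sorts each score into four bands: "no difficulty (0), mild difficulty (< 4), moderate difficulty (4 - <8), and sever difficulty (8-10". The six scores are summed to a 0-60 total, which has bands of its own. The Statistical plan sets one rule for numerical data, "comparison of numerical variables between the study groups was done using a student t test for independent samples", and names the pain and healing scores under it. For categorical data, "the chi-square test was performed (including statistical analysis of the difficulties with functional activities; secondary outcome", with an exact test for small expected counts. Tool (B), the pain VAS, has the same four cuts (0, below 4, 4 to below 8, 8-10).

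**Infection.** Operational definition of terms assigns both healing (a primary outcome) and infection (a secondary outcome) to the REEDA scale. Tool (D) scores five components 0-3 and bands the 0-15 total: 0-2 is good healing without infection, 3-5 moderate, 6-8 mild, and 9-15 poor healing with infection. REEDA is scored at the initial assessment, at six hours and on day 7. No time point is named for infection.

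**The concern.** Two scales of the same form and with the same cuts are sent to different tests, and no reason is given. Pearson chi-square on four ordered bands would give the same answer if the bands were shuffled, and it treats a score of 4.1 like one of 7.9. The hypothesis is directional (better outcomes under the protocol), so order carries the information of interest. At a moderate effect, the planned test could miss a real functional benefit more often than it finds one, and the null result could be read as no benefit.

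For infection, the stake is interpretation. A reader who sees a healing result and an infection result will take them as two pieces of evidence, although both come from one total. Two analysts could also count women scoring 3-8 differently.

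**Working it through.** **1. What is tested.** The Statistical plan mentions neither bands nor single activities. Tool (C) defines no categories other than the bands, and Outcome measures lists the activities singly. A chi-square test on the four bands of each activity is therefore the likely reading, by inference. Whether the 0-60 total is also tested in bands is not stated.

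**2. Inputs.** From the documents: 50 women per arm ("randomly assigned to either study group (50) women or control group (50) women"), two-sided 0.05, and the four bands. Not in the documents: any mean, SD or band frequency for functional difficulty. The Sample section's effect size of 80% is tied to no outcome, so d=0.5 and d=0.8 are illustrations. The plan gives no power figure for this outcome to reproduce.

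**3. One case by hand.** Assume control scores N(5, 2) and treated scores N(4, 2), so d=0.5.

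- *t test.* Noncentrality = d × √(n/2) = 0.5 × √25 = 2.5, with 98 df and critical value 1.984. Power is about **70%**. At d=0.8 the noncentrality is 4.0 and power about 98%.
- *Chi-square on bands.* Noncentrality λ = n × Σ (p − q)²/(p + q), with n = 50.

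| Band | Control p | Treated q | (p − q)²/(p + q) |
|---|---|---|---|
| 0 | 0.006 | 0.023 | 0.0094 |
| below 4 | 0.302 | 0.477 | 0.0392 |
| 4 to below 8 | 0.625 | 0.477 | 0.0197 |
| 8-10 | 0.067 | 0.023 | 0.0217 |

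The last column sums to 0.0901, so λ = 50 × 0.0901 = 4.50. With 3 df and critical value 7.81, power is about **40%**.

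**4. Range of cases.** Simulated normal scores clipped to 0-10; control means 2, 3, 4, 5, 6; SDs 1.5, 2.0, 2.5; the whole distribution shifted by d.

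| d | Chi-square on bands | Ordered (linear-by-linear) test on bands | t test on score |
|---|---|---|---|
| 0.5 | 35%-48% | 46%-62% | 64%-71% |
| 0.8 | 76%-88% | 86%-95% | 94%-99% |

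The chi-square column applies the exact test when an expected count is below 5. Repeat runs with Pearson alone moved the ends of the ranges by one or two points. The chance of missing the effect is thus 52%-65% instead of 29%-36% at d=0.5, and 12%-24% instead of 1%-6% at d=0.8. Put through the t-test power formula, the chi-square power is what a t test would have with about 21-30 (d=0.5) or 23-32 (d=0.8) women per arm instead of 50. With no true difference, rejection was 4.8%-5.3% for the banded test and 5.0%-5.6% for the t test.

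**5. A case that goes the other way.** Suppose 10% of control and 30% of treated women score exactly 0, and non-zero scores are unchanged (mean 3, SD 2). Chi-square then has about 60% power and the t test about 32%. If the non-zero mean also falls from 3 to 2.5, the two are nearly level (about 63% and 66%). With zeros in 20% and 40%, and the same fall in the mean, the t test is ahead again (about 60% against 50%).

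**6. Infection.** There are 16 possible REEDA totals (0-15). Totals 0-2 (three values) are labelled free of infection and totals 9-15 (seven values) infected. The remaining 16 − 3 − 7 = 6 values, 3 to 8, have no infection status. A total of 9 can arise as redness 3 + edema 3 + ecchymosis 3 + discharge 0 + approximation 0. A woman can therefore be labelled infected with no discharge and a fully approximated wound.

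**The case against.** The strongest objection is that the functional part concerns efficiency on a secondary outcome. A reader might infer that the chi-square test is wrong or biased. It is not: its error rate is correct, and both primary outcomes are already planned for t tests. This stands and is why the point is minor.

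A reader might also infer that the banded test always loses. Step 5 shows otherwise: direction as well as size depends on how the protocol changes the scores, and the documents do not say. By day 5 a shift to no difficulty is conceivable. Nor do the documents support a claim that power on the 0-60 total is near zero. That needs an SD of about 4, whereas six completely uncorrelated activities with SD 1.5-2.5 already give √6 × 1.5 = 3.7 to √6 × 2.5 = 6.1, and positive correlation gives more.

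Practicality is a fair objection too. Women are to mark the scale, yet function is assessed only by telephone, and the training described before discharge covers only the pain VAS. If a call yields just a verbal band, a categorical analysis is appropriate. Against that, pain VAS values are to be collected at the same calls, so a number is evidently thought obtainable.

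On infection, it is tempting to call it the healing result under a second name. That goes too far: a mean score and a proportion above a cut can disagree. Reading totals 0-8 as uninfected, and day 7 as the time point, is natural, but neither is written.

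**Conclusion.** Both parts hold, at different weights.

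**Functional activities: minor.** On the likely reading, a valid test uses less information than the instrument provides. The loss is about 20-30 percentage points of power at d=0.5 and roughly 10-20 at d=0.8, provided scores shift as a whole with the assumed means and SDs. It can vanish or reverse if the effect is mainly on the share at exactly 0. Type I error and the primary analyses are unaffected.

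**Infection: moderate.** This rests on the text alone. The only criterion is a band of the total already used for primary healing, 6 of 16 totals have no infection status, and the infected band can be reached through redness, edema and ecchymosis alone. A reported infection difference is therefore not independent evidence.

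**What to change.** **Functional activities.** Compare the 0-10 activity scores and the 0-60 total with the independent-samples t test already planned for pain. Report the bands, including the share at 0, as frequencies and percentages. State how the score is obtained by telephone; if only a band can be obtained, use an ordered (linear-by-linear) test. Name the main call among 24 hours, day 3 and day 5, because 6 activities × 3 calls makes 18 comparisons under either test.

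The cost is a few sentences and a numeric value at each call, with no added women or visits. Power is lost if the effect is confined to zeros, which the descriptive bands would show. The Statistical plan is written in the past tense: if the data have been analysed, disclose the change as post hoc and show the chi-square result beside it.

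**Infection.** Either report REEDA 9-15 as poor healing, do not present it as a separate infection finding, and disclose that a listed secondary outcome has been relabelled; or, if collection is still open, record infection as its own defined yes/no item at the existing day-7 visit. The first costs a disclosure and the loss of a named outcome; the second, one line on a form.
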